5.6. Analyses of Efficacy Variables

The primary efficacy analyses for all the efficacy endpoints will be conducted at Week 28 (visit 16 with a window of -7/+30 days) using the mFAS population. As supportive evidence, the same analysis approach will be repeated with the FAS population at visit 16. The efficacy analyses at visit 22 will be based on the FAS-maintenance population. The analyses of efficacy variables are described in the subsections below and summarized in Section 10.1.

CONFIDENTIAL

Page 39 of 86

5.6.1. Analysis of Primary Efficacy Variable

This primary endpoint will be analyzed using the Cochran-Mantel-Haenszel (CMH) test adjusted by randomization stratification factors (screening peanut-specific IgE level [\leq 100 kUA/L or >100 kUA/L] and baseline body weight [<30 kg, \geq 30 kg and <60 kg, or \geq 60 kg]) to assess the treatment difference in the proportion of responders (i.e., those who "pass" a post up-dosing DBPCFC with 2044 mg [cumulative] peanut protein at visit 16 [Week 28 with a visit window of -7/+30 days]) in the mFAS.- Estimate of treatment difference, p-value, and the 2-sided 95% confidence interval using CMH test will be provided. The number and percent of subjects at each dose level for highest tolerated peanut protein dose at post up-dosing DBPCFC will also be summarized.

The primary estimand of interest for the primary endpoint is described as follows, based on intercurrent event(s) strategy and missing data handling methods:

- The treatment policy strategy will be implemented for the intercurrent event of the treatment discontinuation. The data collected after the patient discontinued treatment will be included in the analysis.
- Missing data for post up-dosing DBPCFC at visit 16 will be handled according to the reason for missingness as follows:
 - If a subject misses the post up-dosing DBPCFC at visit 16 due to COVID-19, the missing data will be imputed by multiple imputation (MI) method for 10 times utilizing available post up-dosing DBPCFC data at visit 16. The MI will utilize logistic regression method with treatment group and randomization stratification.
 - If a subject does not have available DBPCFC data with peanut protein at visit 16 due to reasons not related to COVID-19, this subject will be considered as a nonresponder at visit 16.

Each of complete datasets after the above steps will be analyzed by the CMH test. The SAS MIANALYZE procedure will then be used to generate valid statistical inferences by combining results using Rubin's formula (Rubin, 1987).

Sensitivity analyses will include an analysis of the subset of subjects with available visit 16 DBPCFC data with peanut protein.

The supportive analyses based on FAS and PPS will be performed using primary analysis method.

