A retrospective cohort analysis was also performed to evaluate the safety and efficacy profile of AR101 in relation to baseline peanut-specific IgE. Subjects were grouped by peanut-specific IgE levels of $\leq 100 \text{ kUA/L}$ or >100 kUA/L. All subjects in both groups tolerated at least 443 mg cumulative of peanut protein. However, the 2 groups had different tolerance to higher doses of peanut-specific protein: 1043 mg of cumulative peanut protein was tolerated by 21 subjects (91%) in the $\leq 100 \text{ kUA/L}$ group and 15 subjects (88%) in the >100 kUA/L group; 2043 mg of cumulative peanut protein was tolerated by 17 subjects (74%) in the $\leq 100 \text{ kUA/L}$ group and 7 subjects (17%) in the >100 kUA/L group (Wang 2016).

In the phase 3 AR101 study (PALISADE) in which the prespecified primary analysis was children aged 4 to 17 years (n=496) with peanut allergy, subjects were started on an oral peanut dose of 3 mg on a single day and were then escalated to a maintenance dose of 300 mg/day during an up-dosing period of approximately 6 months, which was followed by a 6 month double-blind maintenance phase. The primary endpoint was the proportion of subjects tolerating 1043 mg (cumulative) peanut protein in the exit DBPCFC; 67.2% of the 372 subjects (ITT) treated with peanut OIT tolerated 1043 mg (cumulative) peanut protein compared to 4.0% of the 124 subjects treated with placebo. Those tolerating 2043 mg (cumulative) peanut protein, a key secondary efficacy endpoint, were 50.3% and 2.4% for peanut OIT and placebo, respectively. Of the AR101-treated subjects, a total of 76 (20.4%) discontinued, with 46 (12.4%) related to AEs. Treatment with AR101 was associated with a marked reduction in the IgE/IgG4 ratio from approximately 100 to <10, whereas an increase was noted in the subjects treated with placebo. Similarly, wheal size in the skin prick test (SPT) was reduced compared to placebo by AR101 treatment (PALISADE Group of Clinical Investigators, 2018).

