11.4.3.1. Primary Efficacy Analysis

The primary endpoint will be analyzed using the Cochran-Mantel-Haenszel test adjusted by randomization stratification factors to assess the treatment difference in the proportion of responders (ie, those who "pass" a post up-dosing DBPCFC with 2044 mg [cumulative] peanut protein at visit 16 [week 28 with a visit window of -7/+30 days]) in the mFAS. Estimate of treatment difference, p-value, and the 2-sided 95 % confidence interval will be provided.

In addition, the primary efficacy endpoint will be performed on the FAS as a supportive analysis.

If a subject does not have available post up-dosing DBPCFC data at visit 16, the subject will be considered as a non-responder regardless of reasons for missing data.

Sensitivity analyses will include an analysis of the subset of subjects with available post up-dosing DBPCFC data from visit 16.

Subgroup analysis (eg, by baseline weight group) will also be performed.

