2.2. Statistical Hypothesis

The primary efficacy endpoint is the proportion of subjects who achieve a cumulative dose of 2044 mg peanut protein during a post up-dosing DBPCFC at visit 16. The comparison between the dupilumab + AR101 arm and the placebo + AR101 arm will be made.

Let p_D and p_P be the true proportions of subjects who achieve a cumulative dose of 2044 mg of peanut protein during a post up-dosing DBPCFC at visit 16 in the treatment arms of dupilumab + AR101 and placebo + AR101, respectively. The following hypothesis for the superiority testing will be tested at the 5% 2-sided significance level for the up-dosing phase:

H0: $p_D = p_P$, i.e., the proportion of subjects who achieve a cumulative dose of 2044 mg peanut

protein during a DBPCFC at visit 16 is the same between dupilumab + AR101 arm and the placebo + AR101 arm

against the alternative

Ha: $p_D \neq p_P$, i.e., the proportion of subjects who achieve a cumulative dose of 2044 mg peanut protein during a DBPCFC at visit 16 are different between the dupilumab + AR101 arm and the placebo + AR101 arm

CONFIDENTIAL

Page 13 of 86

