2.3. Sample Size and Power Considerations

It is assumed that the proportion of subjects who achieve a cumulative dose of 2044 mg of peanut protein during a post up-dosing DBPCFC at visit 16 in placebo plus AR101 arm will be 40%, based on an Aimmune presentation at the 2018 American Academy of Allergy, Asthma & Immunology–World Allergy Organization Joint Congress; with the proportion of subjects in dupilumab plus AR101 arm assumed to be 65%, which is considered to be clinical meaningful benefit by adding on dupilumab treatment. A sample size of approximately 156 subjects (104 in dupilumab plus AR101 and 52 in placebo plus AR101) will have 80% power to detect the treatment difference of 25% between placebo plus AR101 and dupilumab plus AR101 at the 2-sided 5% significance level (the minimum significant difference is approximately 17.8%). The sample size calculations were done by Fisher exact test using nQuery (7.0).

[figure not shown]
Approximately 122 subjects who undergo the post up-dosing DBPCFC at Week 28 (visit 16 with a window of -7/+30 days) as per protocol or discontinue from study prior to Week 28 (visit 16 with a window of -7/+30 days) will be included in the primary efficacy analysis. These subjects receive AR101 dose escalation per the original protocol's 24-week up-dosing schedule. The minimum significant difference with approximately 122 subjects is approximately 20.7% between placebo plus AR101 and dupilumab plus AR101 assuming placebo plus AR101 treatment effect is 40% at the 2-sided Fisher exact test with 5% significance level.

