4. ANALYSIS VARIABLES

4.1. Demographic and Baseline Characteristics

The following demographic and baseline characteristics variables will be summarized:

- Demographic variables
 - Age at screening (year)
 - Age group (≥ 6 to <12 years; ≥ 12 to ≤ 17 years)
 - Sex (Male, Female)
 - Race (White, Black or African American, Asian, American Indian or Alaska Native, Native Hawaiian or Pacific Islander, Other)
 - Ethnicity (Hispanic or Latino, Not Hispanic or Latino)
 - Baseline weight (kg)
 - Baseline weight category ($<30 \text{ kg}, \geq 30 \text{ kg}$ and $<60 \text{ kg}, \geq 60 \text{ kg}$)
 - Baseline height (m)
 - Baseline Body Mass Index (BMI) (kg/m²)
- Baseline characteristics
 - Duration of peanut allergy diagnosis (year)
 - Age at peanut allergy onset (year; <5, ≥ 5 and <10, ≥ 10 and ≤ 17)
 - Number of co-morbid atopic diseases (atopic dermatitis, asthma, nasal polyps, allergic rhinitis or eosinophilic esophagitis)
 - Baseline Fractional Exhaled Nitric Oxide (FeNO) value
 - History of atopic dermatitis (Yes, No)
 - Duration of atopic dermatitis disease with grouping (year; <=1 and >1)
 - Eczema Area and Severity Index (EASI) score for subjects with atopic dermatitis
 - History of asthma (Yes, No)
 - Asthma Control Questionnaire (ACQ-5) score for subjects with asthma
 - Baseline Food Allergy Quality of Life Questionnaire (FAQLQ) score for different types of FAQLQ form
 - Screening serum peanut-specific IgE
 - Screening serum peanut-specific IgG4
 - Screening serum total IgE
 - Screening peanut-specific IgG4/sIgE ratio

- Screening peanut-specific IgE level (≤100 kUA/L, >100 kUA/L)
- Baseline predicted FEV1 (L)
- Baseline percent predicted FEV1 (%)
- Baseline predicted FVC (L)
- Baseline percent predicted FVC (%)
- Maximum tolerated dose of peanut protein at screening DBPCFC
- Use of epinephrine at screening DBPCFC (Yes, No)
- Normalized mean peanut wheal diameter at screening SPT

Note: Normalized mean peanut wheal diameter is defined by mean peanut wheal minus mean saline wheal.

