5.6.2. Analysis of Secondary Efficacy Variables

Continuous Endpoints at visit 16

Change in the cumulative tolerated dose (log transformed) of peanut protein during a DBPCFC from baseline at visit 16 will be analyzed using analysis of covariance (ANCOVA) with treatment as the main effect, stratification variables and baseline tolerated cumulative amount of peanut protein DBPCFC (log transformed) as covariates. If subjects do not tolerate any dose level, they will be assigned a cumulative tolerated dose of 1 mg prior to converting to the log scale. The least-squares (LS) mean for each treatment group with its corresponding standard error (SE), the LS mean difference between treatment group and its corresponding SE and 95% CI, and the p-value corresponding to the between-treatment-group difference will be reported. In addition, change the

CONFIDENTIAL

Page 40 of 86

cumulative tolerated dose of peanut protein during a DBPCFC at visit 16 will be based on a non-parametric analysis using the van Elteren test.

Missing data for post up-dosing DBPCFC at visit 16 will be handled according to the reason for missingness as follows:

- If a subject misses the post up-dosing DBPCFC at visit 16 due to COVID-19, the missing data will be imputed by MI method for 10 times utilizing available post up-dosing DBPCFC data at visit 16. The MI will utilize regression method with treatment group, randomization stratification, and baseline tolerated cumulative amount of peanut protein DBPCFC (log transformed).
- If a subject does not have an available DBPCFC at visit 16 due to reasons not related to COVID-19, the baseline value at screening DBPCFC will be used to impute the missing post up-dosing DBPCFC data at visit 16.

Each of the complete datasets after the above steps will be analyzed by the ANCOVA. The SAS MIANALYZE procedure will then be used to generate valid statistical inferences by combining results.

Two sensitivity analyses will be performed as below to assess the robustness of results:

- Completed cases will be conducted regardless the rescue medication used.
- MI method: the missing data will be imputed by MI method utilizing available post updosing DBPCFC data at visit 16. The MI will utilize the same regression method as the above.

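### The primary CMH test is valid but omits baseline challenge threshold and within-stratum peanut IgE; adding both offers a modest, assumption-dependent gain in power

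*SAP*

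**What the plan says.** Protocol 11.4.3.1 and SAP 5.6.1 agree on the primary test. The protocol has "The primary endpoint will be analyzed using the Cochran-Mantel-Haenszel test adjusted by randomization stratification factors". The SAP has "This primary endpoint will be analyzed using the Cochran-Mantel-Haenszel (CMH) test adjusted by randomization stratification factors" and names the factors: screening peanut-specific IgE (at or below, or above, 100 kUA/L) and baseline weight in three groups, so six strata. Under SAP 5.6.1, a challenge missed because of COVID-19 is imputed by a logistic model with treatment and those strata only.

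The first secondary endpoint, change in log cumulative tolerated dose, is read from the same visit 16 challenge. SAP 5.6.2 analyses it by ANCOVA with the stratification variables and "baseline tolerated cumulative amount of peanut protein DBPCFC (log transformed) as covariates", and puts the same baseline value in its imputation model.

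Both candidate covariates are planned data. SAP 4.1 lists "Maximum tolerated dose of peanut protein at screening DBPCFC" and screening serum peanut-specific IgE among the baseline characteristics. No primary, supportive or sensitivity analysis of the primary endpoint uses the threshold or continuous IgE. SAP 5.11 relates baseline IgE to passing 2044 mg, but only in an exploratory logistic model.

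**The concern.** Two endpoints from one challenge are handled with different amounts of baseline information, and the gatekeeping endpoint gets less. Under Protocol 11.4.3.3 and SAP 5.6.3, the first secondary endpoint supports an inferential conclusion only if the primary is significant at 0.05. The primary analysis is planned on about 122 subjects, whereas the 80% power statement refers to 156. If baseline threshold, or IgE within its two strata, predicts passing 2044 mg, then adjusting for them narrows the interval for the treatment difference at no cost in subjects. A COVID-19-missing challenge would also be imputed from better information.

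**Working it through.** **1. The plan's own figure.** SAP 2.2: the hypothesis "will be tested at the 5% 2-sided significance level for the up-dosing phase". SAP 2.3: the pass rate "at visit 16 in placebo plus AR101 arm will be 40"%, against 65% on dupilumab. 104 + 52 subjects "will have 80% power to detect the treatment difference of 25" points by the Fisher exact test.
- Summing both binomials over all tables with two-sided Fisher p below 0.05 gives 81.1% power at 104 vs 52 (stated 80%).
- The minimum significant difference by enumeration is 18.3 points (stated about 17.8).
- At 122 subjects, 2:1 allocation suggests 81 vs 41 (assumed). The minimum significant difference is 20.2 to 20.3 points there and 21.0 at 82 vs 40 (stated about 20.7).
- No power is stated for 122. Fisher power at 81 vs 41 is 72.2%, so 81.1 - 72.2 = 8.9 points are lost with the 34 subjects.

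**2. What the documents show about prognosis.** Protocol 3.2.1 reports a cohort split at 100 kUA/L and says "However, the 2 groups had different tolerance to higher doses of peanut-specific protein".
- Lower IgE group: 17 tolerated 2043 mg, printed as 74%, so n = 23.
- Higher IgE group: 7 subjects, printed as 17%. In the same group 15 subjects are 88%, which implies n = 17, so 7/17 = 41%. That 41% is a reconstruction; the protocol prints 17%.
- Odds ratio = (17 x 10)/(6 x 7) = 4.05; log odds ratio 1.40; Fisher p = 0.053 on 40 subjects.

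This contrast lies between the two strata CMH already uses. Nothing is reported on IgE within a stratum, or on baseline threshold.

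**3. Range of the threshold.** Inclusion criterion 3 requires a reaction at or before the 100 mg dose, so the most that can be tolerated is 1 + 3 + 10 + 30 = 44 mg. SAP 5.6.2 sets subjects tolerating nothing to 1 mg. The covariate can take only four values: 1, 4, 14 or 44 mg.

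**4. Rough size by arithmetic.** Pooled normal approximation at 81 vs 41:
- Pooled rate = (81 x 0.65 + 41 x 0.40)/122 = 0.566
- SE under the null = sqrt(0.566 x 0.434 x (1/81 + 1/41)) = 0.0950
- SE under the alternative = sqrt(0.65 x 0.35/81 + 0.40 x 0.60/41) = 0.0931
- Power = Phi((0.25 - 1.96 x 0.0950)/0.0931) = 75.4%

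If the covariates explain a further share R2 of outcome variance beyond the strata, both SEs shrink by sqrt(1 - R2). R2 of 0.02, 0.05, 0.10 and 0.15 gives 76.2, 77.5, 79.7 and 81.9%.

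Which R2 is plausible is unknown. As an anchor, assume IgE acts linearly on the logit scale, scaled to the 74% vs 41% gap. Total R2 is then 0.157, of which the split already captures 0.109 (about two thirds). That leaves 0.048, worth about 2 points.

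**5. The proposed test.** Let d be the vector of treatment differences in (pass, log threshold, log IgE), averaged over strata with Mantel-Haenszel weights n1 x n0/(n1 + n0), and V its within-stratum covariance. The adjusted difference is d_y - V_yx V_xx^-1 d_x, with variance V_yy - V_yx V_xx^-1 V_xy.

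Simulated power at 81:41 with six strata and the four-level threshold (its distribution and the effect sizes are assumed):

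| Assumed prognostic pattern | Plain CMH | Adjusted | Change |
|---|---|---|---|
| None | 74.8% | 74.3% | -0.5 |
| IgE step at 100, threshold uninformative | 78.2% | 77.4% | -0.8 |
| IgE step, threshold log OR 0.3 per SD | 78.0% | 77.7% | -0.3 |
| IgE linear (near 74/41), threshold uninformative | 77.9% | 79.5% | +1.6 |
| IgE linear, threshold 0.3 per SD | 77.7% | 79.8% | +2.1 |
| IgE linear, threshold 0.5 per SD | 78.0% | 81.0% | +3.0 |
| Strong threshold effect | 78.1% | 83.7% | +5.6 |

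The five middle rows use 8,000 trials each, a Monte Carlo error of about 0.5 points per figure. The first and last rows come from a separate set of runs, in which the IgE step alone gave 79.1 vs 78.4%, two middle scenarios gave 77.8 vs 79.5% and 78.8 vs 81.5%, and null size was about 5.1%.

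A standardised risk difference from a logistic model gives similar gains (78.7 to 81.3% with linear IgE alone), but its null rate was 5.5% in 10,000 runs.

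**The case against.** The strongest reply is that nothing is wrong. CMH by the randomization factors matches the allocation, is stated alike in protocol and SAP, and is valid. Sizing used an unstratified Fisher test, so the power claim leaned on no covariate, and CMH already does better than Fisher at 81 vs 41. Baseline adjustment is routine for a change score such as the first secondary endpoint; passing 2044 mg is not a change score. The only prognostic data support the existing IgE split, and the threshold's range is cut by entry. If IgE matters only as a step at 100, adjustment loses a little.

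All of that stands, and it limits the size of the point. It does not remove it: the adjusted test holds its size, its downside is under 1 point, and imputing one missing challenge from less information for the primary than for the secondary has no stated reason.

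Two stronger readings are tempting. A reader might infer from the secondary model that the primary test is inconsistent or biased; the documents do not support that, since CMH is valid without the covariates. A reader might also take the 74% vs 41% contrast as proof that continuous IgE would add much power; it speaks only to the split already in the test.

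**Conclusion.** This is a missed efficiency option, not an error. At 81:41 the expected change in power is about -1 to +6 points, roughly 1 to 3 in middle scenarios, with type I error near 5%. It rests on the assumed 81:41 split, the planning rates of 40% and 65%, an assumed threshold distribution, and a prognostic strength that the documents do not give. Some scenarios bring power back to about 80%, but adjustment should not be read as making up for the move from 156 to about 122 subjects, which costs 8.9 points by Fisher and is a separate matter.

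Nor do the inclusion criteria guarantee both covariates. Criterion 4 accepts IgE and/or skin prick test; screening IgE is available because it is a stratification factor. SAP 10.6 foresees peanut IgE not collected at screening and a missing screening-challenge criterion.

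**What to change.** Before unblinding:

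- In SAP 5.6.1, with an aligned sentence in Protocol 11.4.3.1, make the primary test the randomization-based covariate-adjusted CMH. Use the same six strata and Mantel-Haenszel weights, with log baseline cumulative tolerated dose and log screening peanut IgE as covariates. Report the adjusted risk difference with its 95% confidence interval, and say which variance feeds the test and which the interval.
- Add both covariates to the logistic imputation model in SAP 5.6.1.
- Pool the adjusted risk difference and its standard error across imputations by Rubin's rules.
- State a simple rule, blind to treatment, for a missing baseline covariate.
- Keep the plain stratified CMH as the supportive analysis.

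The cost is some SAP text, the protocol sentence and programming, with no new data. Protocol 11 allows SAP revision, with the final version due before database lock. The statistical price is a loss of under 1 point of power if the covariates add nothing beyond the strata.

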8.3.2. Study Drug Discontinuation

Subjects who permanently discontinue from study drug and who do not withdraw from the study will be asked to return to the clinic for all remaining study visits per the visit schedule. If dupilumab study drug is permanently discontinued, subject will also discontinue AR101 and vice versa.

Subjects who permanently discontinue from study drug and who opt to withdraw from the study will be asked to complete study assessments, per Section 13.

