4.5. Efficacy Variable

4.5.1. **Primary Efficacy Variable (s)**

The primary endpoint in this study is:

• Proportion of subjects treated with dupilumab plus AR101 vs placebo plus AR101 who "pass" a post up-dosing DBPCFC with 2044 mg (cumulative) peanut protein at visit 16

Double-blind placebo-controlled food challenge (DBPCFC)

At visit 16, under intensive monitoring, all subjects who achieve 300 mg/day AR101 during the up-dosing phase for at least 2 weeks will undergo a post up-dosing DBPCFC up to 2044 mg (cumulative) peanut protein or placebo to assess desensitization. At visit 22, all subjects who maintain 300 mg/day AR101 will undergo a post maintenance DBPCFC up to 2044 (cumulative) peanut protein or placebo to assess desensitization. The subject's sensitivity to peanut allergen is defined as the dose at which the subject experiences allergic reactions. All symptoms and signs will be evaluated and rated based on a standardized oral food challenge scoring system (CoFAR). Up-dosing during the DBPCFC will be stopped when the principal investigator (or designee) finds symptoms and/or signs that indicate a definite objective (Grade 1 [mild]) allergic reaction (CoFAR grading system) has occurred based on clinically significant changes in reported symptoms, physical findings, or vital signs that the subject is experiencing to the challenge material. Vital signs will be assessed every 15 to 30 minutes. In addition, subjects will be considered to have dose-limiting reactions if they experience any mild subjective reactions requiring pharmacologic intervention and/or any moderate/severe reaction.

The DBPCFC will consist of 8 doses (peanut protein or placebo), given every 15 to 30 minutes: 1, 3, 10, 30, 100, 300, 600, 1000 mg, up to 2044 mg peanut protein (cumulative). Both peanut and oat protein will be concealed in a food that masks the taste. The food challenge will be performed on different days (1-day placebo [oat] protein, 1-day peanut protein, with order determined at random) at least 24 hours, but not more than 7 days apart, and not within 24 hours of a dose of study drug. Subjects will be considered to have passed the DBPCFC if they do not experience any objective Grade 1 (mild) reaction by CoFAR grading system. If the subject experiences reactions,

Regeneron Pharmaceuticals, Inc. Statistical Analysis Plan

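### SAP 5.6.1 calls the primary estimand treatment policy, but for subjects who stop before two weeks at 300 mg/day AR101 its rules estimate a composite

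*SAP*

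**What the plan says.** SAP 5.6.1 describes the primary estimand in two parts. On discontinuation it states "The treatment policy strategy will be implemented for the intercurrent event of the treatment discontinuation" and adds "The data collected after the patient discontinued treatment will be included in the analysis". It then handles a missing visit 16 challenge by reason. For COVID-19: "If a subject misses the post up-dosing DBPCFC at visit 16 due to COVID-19, the missing data will be imputed by multiple imputation", using treatment group, randomization strata and the challenges that were observed. Otherwise, "this subject will be considered as a nonresponder at visit 16". Protocol 11.4.3.1 has a single rule, "the subject will be considered as a non-responder regardless of reasons for missing data", although Protocol Section 11 leaves COVID-19 handling to the SAP.

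Who is challenged is fixed elsewhere:

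- SAP 4.5.1, matching Protocol 6.1: "all subjects who achieve 300 mg/day AR101 during the up-dosing phase for at least 2 weeks will undergo a post up-dosing DBPCFC".
- Protocol 8.3.2: "If dupilumab study drug is permanently discontinued, subject will also discontinue AR101 and vice versa". The same section asks subjects who stop drug but remain in the study to keep attending visits.
- SAP 2.4 counts anyone who misses the two-week condition as a non-responder and makes no exception for COVID-19.
- The schedules of events (Protocol Table 4, SAP Table 3) mark the challenge at visits 16, 22 and 25, not at the early termination visit.

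The primary analysis set is defined in two ways. SAP 3.1 admits to the mFAS only subjects who undergo the week 28 challenge. SAP 2.3 and Protocol 11.3.1 also admit subjects who leave the study before then.

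**The concern.** A treatment-policy strategy needs an outcome that is measured and used whether or not the subject stopped treatment. In this design most subjects who stop during up-dosing can have no such outcome, because stopping either drug stops both and the challenge requires two weeks at the top dose. Counting them as non-responders is a reasonable choice, but it is a composite strategy, and the SAP does not name it.

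What is at stake is the claim. The sponsor expects dupilumab to make up-dosing more tolerable (Protocol Sections 1 and 3.2.1), so different discontinuation rates by arm are part of the hypothesis. The primary objective nevertheless speaks of improved desensitization. As an illustration with assumed figures, suppose 60% of challenged subjects pass in both arms:

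- With 80% challenged on placebo and 90% on dupilumab, the responder rates are 0.60 × 0.80 = 48% and 0.60 × 0.90 = 54%. That is a 6-point difference produced by tolerability alone.
- With 95% challenged on dupilumab, the rate is 0.60 × 0.95 = 57%, a 9-point difference.

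This would be a real benefit, but a different one from what a treatment-policy label implies.

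**Working it through.** **1. The plan's own figure.** Inputs from SAP 2.3: 52 and 104 subjects, pass rates of 40% and 65%, Fisher exact test, two-sided 5%. Summing the binomial probabilities of all outcome pairs with Fisher p ≤ 0.05 gives a power of 81.1%, against 80% stated. The figure reproduces. The estimand label does not enter the calculation, so relabelling leaves it unchanged.

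**2. What happens to a subject who stops.** On the planned schedule (Protocol Table 2), 300 mg starts at week 24, so the two-week condition is met at about week 26. Visit 16 is at week 28, with a window of -7/+30 days.

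| Situation | Visit 16 challenge | Outcome under the SAP | Strategy in effect |
|---|---|---|---|
| Stops before two weeks at 300 mg/day, non-COVID reason | None | Non-responder (2.4, 5.6.1) | Composite |
| Does not reach the condition because of COVID-19 | None | Non-responder in 2.4; multiple imputation in 5.6.1 | Not determined |
| Stops after meeting the condition, stays in study, is challenged | Possible | Observed result is used | Treatment policy |
| Still on treatment, misses the challenge because of COVID-19 | Missing | Multiple imputation | No discontinuation; missing-data handling |

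SAP 5.4 lists COVID-19 among the reasons for discontinuing treatment. A subject in the second row may therefore also fall under the treatment-policy sentence, which makes three rules for one subject.

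**3. Size of the mislabelling.** Let d be the share of an arm that stops before the condition is met, and q the share of those subjects who would pass if challenged. If p is the composite rate, the treatment-policy rate is p + d × q. The composite difference therefore exceeds the treatment-policy difference by q × (d placebo − d dupilumab).

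Inputs: p = 40% and 65% are the planning rates in SAP 2.3, taken here as composite rates. For placebo, d = 20% is an assumption, guided by Protocol Section 1, which gives up to 20% unable to complete up-dosing. The values of d for dupilumab and of q are assumptions; the documents give neither. The composite difference is 65 − 40 = 25 points.

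| d placebo / dupilumab | Treatment-policy difference at q = 10%, 20%, 30% | Divergence from 25 points |
|---|---|---|
| 20% / 20% | 25, 25, 25 | 0, 0, 0 |
| 20% / 10% | 24, 23, 22 | 1, 2, 3 |
| 20% / 5% | 23.5, 22, 20.5 | 1.5, 3, 4.5 |

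Largest case: 0.30 × (0.20 − 0.05) = 0.045.

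**4. If the mFAS of SAP 3.1 is applied literally.** Unchallenged discontinuers are then dropped, and each rate becomes p / (1 − d). Placebo is 0.40 / 0.80 = 50.0%. Dupilumab is 0.65 / 0.80 = 81.2%, 0.65 / 0.90 = 72.2% or 0.65 / 0.95 = 68.4%. The differences are 31.2, 22.2 and 18.4 points. That is neither the composite nor treatment policy, and under these assumptions the choice of analysis set matters more than the label.

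**The case against.** The other side has several good points.

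- A reader might infer that no one can be challenged after discontinuing. The documents do not say so. Protocol 8.3.2 keeps such subjects in the visit schedule, and the condition is worded as having achieved 300 mg/day for two weeks, not as being on drug at visit 16. The sentence on later data therefore has a use, and deleting it or failing every discontinuer would override observed passes. This stands.
- A reader might call the COVID-19 imputation a hypothetical strategy. A subject can miss the challenge because of COVID-19 without stopping anything, and SAP 5.6.1 lists the rule under missing data. This stands too; what is lacking is a statement of the assumption and of precedence over SAP 2.4.
- Nothing is concealed. The non-responder rule sits directly beneath the label, and better tolerability is an intended benefit.
- Much of the breakdown is already planned: the analysis of subjects with available challenge data and the table of highest tolerated dose (SAP 5.6.1), the comparison of subjects reaching 300 mg/day (SAP 4.5.2 and 5.6.2), and discontinuations by period and reason (SAP 5.4).

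None of this makes the label correct for subjects who stop before meeting the condition, and none of it settles the COVID-19 rule or the mFAS definition.

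**Conclusion.** The primary estimand is mislabelled for the main group of discontinuers. For those who stop early for non-COVID reasons, the analysis estimates the proportion who reach the challenge and pass it. The mislabelling comes with two conflicts that a programmer could not resolve from the text: SAP 2.4 against 5.6.1 for COVID-19, and SAP 3.1 against 2.3 and Protocol 11.3.1 for the mFAS.

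The divergence of 0 to 4.5 points rests wholly on the assumed discontinuation shares and pass rates. A reader might infer from Protocol 3.2.1 that about one in five primary outcomes is set by rule. The 20.4% reported there for the phase 3 AR101 study covers maintenance as well as up-dosing, the figure in Section 1 is an upper bound, and neither is given by arm for this trial. A reader might likewise build a 15-point artefact from 65% against 90% challenged (0.60 × 0.65 = 39%; 0.60 × 0.90 = 54%). Nothing in the documents supports 35% unchallenged on placebo.

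The planned test and the stated power are not in question here.

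**What to change.** Amend the SAP before unblinding:

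1. In 5.6.1, name a composite strategy for discontinuing before, or not reaching, two weeks at 300 mg/day.
2. Keep the treatment-policy sentence only for challenges observed after later discontinuation, so that observed results are used.
3. State whether the rule in 2.4 or the imputation in 5.6.1 governs a subject who does not reach 300 mg/day because of COVID-19. Describe the imputation as missing-data handling and name its assumption.
4. Restore the discontinuer clause to the mFAS in 3.1 so that it agrees with SAP 2.3 and Protocol 11.3.1. Those definitions speak of leaving the study, so also say where a subject belongs who stops drug, stays in follow-up and is not challenged.
5. Word the conclusion as the proportion who complete up-dosing and pass.

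A by-arm count of not challenged, challenged and failed, and challenged and passed would help readers but is optional. The cost is SAP text and a slightly narrower claim. Trial conduct, clinical rules and the planned test do not change.
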